#### 1.4.3.2 Study AG120-C-001

Study AG120-C-001 is evaluating the safety, PK, PD biomarker patterns, and clinical activity of ivosidenib in participants with advanced AML and related hematologic malignancies that harbor an IDHI mutation. The primary objectives of the study are to assess the safety and tolerability of treatment with ivosidenib administered daily in participants with advanced hematologic malignancies, to determine the MTD and/or the recommended Phase 2 dose of ivosidenib in this population, and to assess the preliminary clinical activity of ivosidenib in participants with relapsed or refractory AML with an IDHI mutation. The initial dosing regimen was BID; based on the favorable PK profile showing a long t/2, BID dosing was discontinued after the first cohort and a QD dosing regimen was implemented. Similar to the AG120-C-002 study, this study is divided into a dose escalation phase, followed by an expansion phase to allow for a more robust evaluation of the safety profile and preliminary assessment of clinical activity. This study is currently ongoing and has served as the basis for the 2018 FDA approval of ivosidenib in relapsed refractory AML. A summary of the data from this study is provided in the Investigator's Brochure for

ivosidenib.

# 1.5 Identified Risks of Ivosidenib

A summary of AEs reported in> 10% of participants overall is presented in Table 25 of the Investigator's Brochure. As of January 16, 2019, 165 (98.2%) of the 168 participants had reported at least one AE. The most commonly reported AEs (> 20% of participants) across all 168 participants were fatigue (33.9%), nausea (29.2%), diarrhea (26.2%), and vomiting (20.2%).

AEs of Grade 3 in severity have been reported in 59 (35.1%) of the 168 participants as of the data cutoff date. Grade 3 AEs reported in> 2 participants included ascites, hyponatremia, and hypophosphatasemia (five participants each); anemia (four participants); and abdominal pain, headache, hyperglycemia, and pulmonary embolism (three participants each).

As of the data cutoff date, AEs leading to discontinuation of study treatment were reported for two participants (cystitis and hyponatremia in one participant and hydronephrosis in the other). All events leading to discontinuation were assessed as unrelated to ivosidenib. No dose-limiting toxicities have been reported in the study and the MTD was not reached.

# 1.6 Nivolumab (BM-936558)

Nivolumab (also referred to as BMS-936558 or MDX1106) is a human monoclonal antibody (mAb, immunoglobulin (lg)G4-S228P) that targets the PD-1 (CD279) cell surface membrane receptor. PD-1 is a negative regulatory molecule expressed by activated T and B lymphocytes. Binding of PD-1 to its ligands, PD-LI and PD-L2, results in the downregulation of lymphocyte activation. Inhibition of the interaction between PD-1 and its ligands promotes immune responses and antigen-specific T-cell responses to both foreign antigens as well as self-antigens. Nivolumab is expressed in Chinese hamster ovary cells and is produced using standard mammalian cell cultivation and chromatographic purification technologies. The clinical study product is a sterile solution for IV administration.

The PK, clinical activity, and safety of nivolumab have been assessed in participants with non-NSCLC, MEL, and clear-cell RCC in addition to other tumor types. Nivolumab is being investigated both as monotherapy and in combination with chemotherapy, targeted therapies, and other immunotherapies.

Opdivo® (nivolumab) is approved for the treatment of unresectable or metastatic MEL in multiple countries including Japan (Jul-2014), the US (Dec-2014), and the European Union (EU) (Jun-2015). Nivolumab is also approved for the treatment of metastatic squamous (SQ) NSCLC in the US (Mar-2015).

The overall safety experience with nivolumab, as a monotherapy or in combination with other therapeutics, is based on experience in approximately 12,300 participants treated to date.

For monotherapy, the safety profile is similar across tumor types. There is no pattern in the incidence, severity, or causality of AEs to nivolumab dose level. In Phase 3 controlled studies, the safety profile of nivolumab monotherapy is acceptable in the context of the observed clinical efficacy and is manageable using established safety guidelines. Clinically relevant AEs typical of stimulation of the immune system were infrequent and manageable by delaying or stopping nivolumab treatment and timely immunosuppressive therapy or other supportive care.

In several ongoing clinical studies, the safety of nivolumab in combination with other therapeutics such as ipilimumab, cytotoxic chemotherapy, anti-angiogenics, and targeted therapies is being explored. Most studies are ongoing and, as such, the safety profile of nivolumab combinations continues to evolve. The most advanced combination under development is the nivolumab and ipilimumab combination therapy, which is approved in participants with unresectable or metastatic MEL and being studied in multiple tumor types. Results to date suggest that the safety profile of nivolumab and ipilimumab and ipilimumab. The nature of the AEs is similar to that observed with either agent used as monotherapy; however, both frequency and severity of most AEs increase with the combination.

Detailed descriptions of the chemistry, pharmacology, efficacy, and safety of nivolumab are provided in the nivolumab Investigator Brochure (1B).

## 1.6.1 Nivolumab Storage

The product does not contain a preservative.

After preparation, store the OPDIVO infusion either:

- at room temperature for no more than 8 h from the time of preparation. This includes room temperature storage of the infusion in the IV container and time for administration of the infusion or
- under refrigeration at 2°C to 8°C (36°F to 46°F) for no more than 24 h from the time of infusion preparation.

Do not freeze.

Detailed descriptions of the chemistry, pharmacology, efficacy, and safety of nivolumab are provided in the nivolumab 1B.

#### 2.0 Trial Objectives and Endpoints

#### 2.1 Objectives

## 2.1.1Primary Objective

The primary objective of the study is:

• To describe the clinical response and six-month progression-free survival of patients treated with ivosidenib in combination with nivolumab

#### 2.1.2Secondary Objectives

The secondary objectives of the study are:

- To determine the safety of ivosidenib in combination with nivolumab
- To summarize longitudinal clinical outcomes of patients treated with ivosidenib in combination with nivolumab

### 2.1.3Exploratory Objective

• To evaluate biomaterial-based biomarkers and determine their association with treatment

response.

### 2.2 Study Endpoints

### 2.2.1 Primary Endpoints

- Response
  - Advanced Solid Tumors: Best overall response by RECIST 1.1 as detailed in {Section 11.8}
     8 weeks after the initiation of treatment
  - Glioma: Best overall Response by Response Assessment in Neuro-Oncology (RANO), Criteria as detailed in (Section 11.9) 8 weeks after the initiation of treatment
- Six-Month Progression Free Survival (PFSG)
  - All tumor types: All tumor types: Survival to six months after the initiation of treatment without objective tumor progression

## 2.2.2 Secondary Endpoints

- The occurrence of dose-limiting toxicity (DLT), as defined in Section 7.5, in patients receiving ivosidenib plus nivolumab.
- Adverse events in patients receiving the combination of ivosidenib and nivolumab based on CTCAEvS.0
- Progression Free Survival (PFS) Survival with freedom from objective tumor progression from time of first treatment until up to 18 months after the last participant has initiated treatment.

## 2.2.3 Exploratory Endpoints

• The association between response biomarkers and clinical outcomes in patients treated with combination ivosidenib and nivolumab.

## 3.0 Investigational Plan

## 3.1 Overall Study Design

This is a Phase II study of orally administered ivosidenib in patients with advanced solid tumors (nonresectable or metastatic) or enhancing gliomas. Participants are required to have a histologically consistent diagnosis of *IDH1* gene-mutated tumor that is not eligible for curative therapy. Participants must have received appropriate standard of care treatment options {in the opinion of the treating investigator).

Each participant's course of treatment will be comprised of the following periods:

**Pre-Treatment/Screening Period: Following informed consent, all potential participants will undergo Screening procedures to determine eligibility within 28 days prior to the start of study treatment on Cycle 1, Day 1 (C1D1), with the exception of baseline radiographic scans, which should be performed within 21 days prior to C1D1. In patients with advanced solid tumors excluding brain tumors, a tumor biopsy will be collected if not done so before screening. A second biopsy will be taken at the end of the first cycle of nivolumab (approximately week 4 \pm 10 days). Additional Screening procedures are detailed in the study calendar in Section 6.1** 

Treatment Period and End of Treatment Visit: Participants who meet all study eligibility criteria will be eligible to start study treatment (criteria detailed in Section 4). Daily study treatment will begin on CIDI with planned concurrent dosing of ivosidenib and nivolumab. Cycles are 28 days (±2 days) in duration and dosing is continuous. Ivosidenib will be dosed daily on 28-day cycles and nivolumab will be infused IV every 28 days. All participants will continue to receive best supportive care according to institutional practice throughout the study, regardless of treatment arm. Study visits will be conducted every other week during Cycles 1-3 (Days 1 and 15), and Day 1 of each cycle thereafter. An end of treatment (EOT) Visit will be performed on the last day of study treatment (within 5 to 33 days of last dose of either study treatment to accommodate for potential dosing delays of up to 28 days).

Dosing		
Drug	ivosidenib	nivolumab
Dose Level 1	500 mg daily	480 mg IV q4
Dose Level -1	250 mg daily	480 mg IV q4

**Schedule of Administration**: Ivosidenib will be administered concurrently with nivolumab beginning on CIDI to patients with an IDHI mutant solid tumor or glioma selected by CUA certified sequencing for IDHI R132 mutations. Should toxicity monitoring suggest and intolerable dose, a dose de-escalation approach will be employed according to the above dose levels. Dosing will be continuous (once daily) on a 28-day cycle. After confirmation of tolerable dose, ivosidenib will be continued throughout the rest of the trial. Nivolumab will be dosed concurrently at 480 mg IV q4 weeks starting on CIDI. After collecting baseline peripheral blood, a research biopsy will also be collected in at least the first 10 patients with advanced solid tumors - ie, not in glioma - in whom a biopsy is deemed safe by the treating physician, pending available funding. Ivosidenib will then be administered concurrently with nivolumab on a Q28 day schedule. A second biopsy will be taken at the end of the first cycle of nivolumab (approximately week 4), pending funding. Treatment with ivosidenib will continue indefinitely per treating investigator discretion.

Nivolumab will be given for up to 1 year. Either agent will be discontinued upon severe toxicity, confirmed disease progression, confirmed pregnancy, death, withdrawal of consent, or if the participant is lost to follow-up.

Radiographic assessment (CT or MRI) for evaluation of disease response will be conducted every 8 weeks (±7 days) from C1D1, independent of dose delays and/or dose interruptions, and/or at any time when progression of disease is suspected. For participants who discontinue study drugs for reasons other than disease progression or start of another anticancer agent, an assessment will be conducted at the EOT Visit. Target and non-target lesion selection and objective tumor response assessments per Response Evaluation Criteria in Solid Tumors (RECIST) vI.1and RANO criteria for glioma patients.

Participants will be assessed at every visit for AEs and concomitant medications, starting from the first dose of study treatment. Toxicity severity will be graded according to the National Cancer Institute Common Terminology Criteria for Adverse Events (NCI CTCAE) version 5.0. Additional physical exam and laboratory will be conducted at each visit as detailed in the study assessments and biomarker table.

Participants may continue with their assigned study treatment until disease progression, development of unacceptable toxicity, confirmed pregnancy, death, withdrawal of consent, the participant is lost to follow-up, or the Lead Principal Investigator (PI) ends the study, whichever occurs first. For participants who are determined to be on ivosidenib upon radiographic disease progression and demonstrate clinical benefit, treating investigators, with consult from the Lead PI, may keep the participants on ivosidenib after the disease progression.

**Post-Treatment Follow-up Visit:** A Post-Treatment Follow-Up Visit for safety will occur 28 days (no more than 33 days) after the last dose of study drug. Every effort must be made to perform protocol-specified evaluations unless consent to participate in the study is withdrawn. Assessments to be performed at the Follow-up Visit are included under study assessments. If a participant's dose is interrupted for 28 days and then the participant discontinues study participation, the EOT Visit will serve as the Post-Treatment Follow-up Visit.

**PFS Follow-up:** Participants who discontinue study treatment for reasons other than disease progression or withdrawal of consent will be followed in PFS follow-up (every 8 weeks through week 48, and every 8 weeks thereafter) until documented disease progression, death, or the initiation of new cancer therapy. If a participant begins a new anticancer therapy during PFS follow-up, information on the new anticancer therapy will be collected.

**End of Study:** End of study is defined as the point in time when all participants have died, withdrawn consent, or been lost to follow-up.

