### 4.2 Exclusion Criteria

Participants who meet any of the following criteria will not be enrolled in the study:

- 1. Received a prior IDH inhibitor.
- 2. Received systemic anticancer therapy or an investigational agent< 2 weeks prior to Day 1). In addition, the first dose of study treatment should not occur before a period?: 5 half-lives (ti/2) of the investigational agent has elapsed.
- 3. For solid tumor patients: received radiotherapy to metastatic sites of disease< 2 weeks prior to Day 1 and for glioma patients have received radiation within 3 months prior.
- 4. For solid tumor patients, have underwent hepatic radiation, chemoembolization, and radiofrequency ablation< 4 weeks prior to Day 1.
- 5. Participants must not have a diagnosis of immunodeficiency or is receiving systemic steroid therapy at a dose of> 10 mg prednisone daily or equivalent at time of first dose of study treatment.
- 6. Participants must not have active autoimmune disease that has required systemic treatment in the past 2 years (i.e., with use of disease modifying agents, corticosteroids or immunosuppressive drugs). Replacement therapy (e.g. thyroxine, insulin, or physiologic corticosteroids replacement therapy for adrenal or pituitary insufficiency, etc.) is not considered a form of systemic treatment.
- 7. Participants must not have a known history of non-infectious pneumonitis that required steroids for treatment.
- 8. Participants must not have evidence of interstitial lung disease.
- 9. For solid tumor patients, have known symptomatic brain metastases requiring steroids. Participants with previously diagnosed brain metastases are eligible if they have completed their treatment and have recovered from the acute effects of radiation therapy or surgery prior to study entry, have discontinued corticosteroid treatment for these metastases for at least 1 week and have radiographically stable disease for at least 1 month prior to study entry.
- 10. Have a history of another primary cancer that is active requiring treatment, progressing or for which the treating investigator believes will make disease assessment unreliable.
- 11. Have evidence of intracranial or intra-tumoral hemorrhage either by MRI or computed tomographic (CT) scan. Participants with resolving post-surgical changes, punctate hemorrhage, or hemosiderin are eligible.
- 12. Underwent major surgery within 4 weeks of Day 1 or have not recovered from post-surgery toxicities.
- 13. Are pregnant or breastfeeding.

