# 6.0 Study Processes and Assessments

### 6.1 Schedule of Events

Table 3 provides the schedule of assessments for this study. Pre-screening or screening for IDH1 will occur via CLIA certified standard of care sequencing. After obtaining written informed consent for the study overall, all participants will undergo Screening procedures to determine eligibility within 28 days prior to the start of study treatment on C1D1. Participants are to attend study center visits as outlined in the Schedule of Assessments (Table 3).

An EOT Visit will be conducted as soon as possible after discontinuing study treatment (within 5 days of last dose of study treatment, if study drug dosing has not been delayed); in addition, participants are to attend a Follow-up Visit 28 days (no more than 33 days) after the last dose of study treatment for final safety assessments. If a participant's dose is held and it is subsequently decided to discontinue treatment, the EOT Visit should be conducted as soon as possible, within 28 days (and no more than 33 days) after the last dose of study treatment for final safety assessments.

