# Target Lesions:

When more than 1 measurable lesion is present at baseline all lesions up to a maximum of 5 total (and a maximum of 2 lesions per organ) representative of all involved organs should be identified as target lesions and measured at baseline.

Target lesions should be selected on the basis of their size (lesions with the longest diameter), be representative of all involved organs, but in addition should be those that lend themselves to reproducible repeated measurements.

Pathological lymph nodes that are defined as measurable and identified as target lesions must have a short axis of 15 mm by CT scan. Only the short axis of these nodes contributes to the baseline sum.

A sum of the diameters (longest for non-nodal lesions, short axis for nodal lesions) for all target lesions will be calculated and reported as the baseline sum diameters. The baseline sum diameters will be used as reference to further characterize any objective tumor regression in the measurable dimension of the disease.

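### The baseline scan may be up to 21 days old while systemic therapy, and radiotherapy to metastases in solid tumors, is barred only for the last 2 weeks, so response can be measured from a scan that predates the last prior treatment

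*Combined protocol and SAP*

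**What the plan says.** **Scan window.** Section 3.1 allows 28 days for screening, "with the exception of baseline radiographic scans, which should be performed within 21 days prior to C1D1". Section 6.1 restates the general window without that exception: "all participants will undergo Screening procedures to determine eligibility within 28 days prior to the start of study treatment on C1D1".

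**Prior treatment (Section 4.2).**
- Exclusion 2, all participants: "Received systemic anticancer therapy or an investigational agent< 2 weeks prior to Day 1". For investigational agents it adds a minimum of five half-lives: "the first dose of study treatment should not occur before a period" of that length has passed.
- Exclusion 3, with separate limits for solid tumors and glioma: "received radiotherapy to metastatic sites of disease< 2 weeks prior to Day 1 and for glioma patients have received radiation within 3 months prior".
- Exclusion 4, solid tumors: "have underwent hepatic radiation, chemoembolization, and radiofrequency ablation< 4 weeks prior to Day 1".

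**Use of the baseline.** Appendix 11.8 says of target lesions: "The baseline sum diameters will be used as reference to further characterize any objective tumor regression". A RECIST partial response is a 30% fall from that sum. RANO in Appendix 11.9 also measures partial response from baseline and requires it to be sustained for at least 4 weeks.

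**Endpoint and rule.** Section 2.2.1 lists response and six-month progression-free survival (PFS6) as separate primary endpoints. Section 8.2.1 counts a participant as positive only with PFS6 and at least a partial response at the 12-week scan. It enrols 18, continues with 17 more if at least 3 are positive, and rejects the 10% null if at least 7 of 35 are positive.

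**The concern.** The baseline scan should describe the tumor after prior treatment has ended and before study treatment begins. Here the two windows do not meet. A participant can be scanned on Day −21, receive a last dose of chemotherapy or a last fraction to a metastasis a few days later, and start on Day 1 in full compliance. Shrinkage from that treatment then counts towards the 30% (RECIST) or 50% (RANO) reduction and is read as a response to ivosidenib plus nivolumab.

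A randomized comparison would share such carry-over between arms. This trial is compared with historical data, so nothing absorbs it. What is at stake is the attribution of individual responses and, to a smaller degree, the false-positive rate of the two-stage rule.

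**Working it through.** **1. Overlap of the windows.** Overlap = scan window − exclusion window, set to zero if negative.

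| Prior treatment | Excluded if given within | Overlap with 21-day scan window |
|---|---|---|
| Systemic therapy, all participants | 14 days | 21 − 14 = 7 days |
| Radiotherapy to metastatic sites, solid tumors | 14 days | 21 − 14 = 7 days |
| Hepatic radiation, chemoembolization, ablation (solid tumors) | 28 days | none (28 > 21) |
| Radiation, glioma | 3 months | none |

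For an investigational agent the five-half-life condition may lengthen the interval and close the gap, but it is tied to the first dose and not to the scan. If the 28-day window of Section 6.1 were applied to scans, the overlap in the first two rows would be 28 − 14 = 14 days.

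**2. Does another provision close the gap?** Inclusion 2 requires that standard options have been used. It does not require progression on them, or a scan after them. Section 5.13.3 bars other anticancer therapy during the study, but its instruction is to stop study treatment, so it addresses participants already on treatment. Exclusion 2 is the specific rule for the time before Day 1.

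**3. The plan's own figures.** With n1 = 18, n2 = 17, continuation at 3 or more and rejection at 7 or more in total:

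P(reject | p) = Σ over x = 3 to 18 of P(X1 = x) × P(X2 ≥ 7 − x), where X1 ~ Bin(18, p) and X2 ~ Bin(17, p).

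- p = 0.10: 0.0474, against the stated 0.05.
- p = 0.30: 0.9016, against the stated 90%.

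The stated design is reproduced.

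**4. Sensitivity to carry-over.** The documents give no rate of carry-over. As an assumption, let it add d percentage points to the true composite rate and put the sum into the same formula.

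| True composite rate | d | Rate used | P(declare success) |
|---|---|---|---|
| 10% | 0 | 0.10 | 0.047 |
| 10% | 1 | 0.11 | 0.072 |
| 10% | 2 | 0.12 | 0.103 |
| 10% | 3 | 0.13 | 0.141 |
| 5% | 0 | 0.05 | 0.001 |
| 5% | 3 | 0.08 | 0.016 |

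The 5% true rate is also an assumption. It is a plausible one: Section 8.2.1 expects response alone to be below 10%, and a composite that requires response and PFS6 together cannot exceed the response rate. On 35 participants, 3 points is 0.03 × 35 ≈ 1 participant who is positive only because of treatment given in a one-week window.

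**The case against.** The strongest reply is that carry-over alone will rarely produce a positive outcome. The participant must show a partial response at the 12-week scan and be alive without progression at six months. In RANO the response must also last at least 4 weeks. RECIST progression is judged from the smallest sum since treatment started, so early carry-over shrinkage lowers the nadir and makes later progression easier to reach. An old baseline can also miss growth before Day 1, which biases against response. All of this stands and limits the effect on the composite. It does not remove it: shrinkage from prior therapy followed by stable disease on study would score as positive, and Section 1.2.1 itself anticipates a cytostatic effect of ivosidenib. Nor does PFS6 protect response where Section 2.2.1 lists it as a primary endpoint in its own right.

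Three stronger readings are tempting and not supported:

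- **The trial's error rate is really 7% to 14%.** Those figures need an assumed carry-over rate and a true rate exactly at the 10% null boundary. They are the unfavourable end of a range.
- **All prior radiotherapy is affected.** Glioma radiation and liver-directed treatment have exclusion periods longer than the scan window.
- **The plan has no rule on irradiated target lesions.** The printed text of Appendix 11.8 has none, but it refers to the full RECIST 1.1 guideline, and the RANO appendix refers to a separate imaging manual. Neither is available here, so the absence is not established.

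**Conclusion.** The mismatch is real and follows from the text: up to 7 days in which systemic therapy (any participant) or radiotherapy to a metastasis (solid tumor) can follow the baseline scan. Response measured from such a scan cannot be attributed cleanly to the study drugs.

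The consequence for the composite test is probably small, and its size cannot be determined from the documents, because neither the share of participants treated in that week nor the resulting shrinkage is given. Under the assumptions shown, the chance of declaring success runs from 0.016 (true rate 5%, 3 points added) to 0.141 (true rate 10%, 3 points added). The stated design figures are correct and need no change. The exposure is greater for response reported by itself, which PFS6 does not filter.

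**What to change.** In Sections 3.1 and 6.1 and in Table 3, require the baseline tumor assessment to be both within 21 days before C1D1 and after the last dose or fraction of any prior anticancer therapy. Schedule the scan accordingly, or repeat it before C1D1 if treatment followed it. In the same edit, reconcile the 28-day window in Section 6.1 with the 21-day scan window in Section 3.1.

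This reduces the overlap to zero and leaves the sample size and decision rule as they are. The cost is an occasional later or repeated screening scan. No change to any exclusion period or eligibility rule is proposed.
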